assessment of the endpoint of Ventilator Free Days (VFDs). Criterion 6 and 7 excludes patients that may have worsening of systemic hypotension due to additional effects of treprostinil. Patients with diffuse alveolar hemorrhage (criterion 3) are excluded because the mechanism of lung injury is different from ARDS/ALI due to infection. Patients with left ventricular systolic dysfunction (criterion 5) are excluded because distinguishing ARDS/ALI from pulmonary edema may be difficult and treprostinil may worsen left heart failure. For exclusion criterion 14: The recently updated clinical protocol for high flow nasal cannula use encourages flow rates beginning at 20 LPM up to 50 LPM. Invasive or non-invasive ventilation are the next options for oxygen requirements beyond 50 LPM. For exclusion criterion 15: Randomized patients are withdrawn from treatment if they require positive pressure ventilation in the form of Bi-level Positive Airway Pressure (BiPAP) or Continuous Positive Airway Pressure (CPAP), or intubation and invasive mechanical ventilation. They will receive supplemental oxygen as needed by the study protocol until that point. Unless they have comfort care only orders written, patients with pneumonia or early ARDS who are DNR receive all forms of supplemental oxygen. Therefore there is nothing in the protocol that precludes a patient who is DNR from participating. If the study drug shows a beneficial effect, the benefit would be relevant to patients who are DNR. Patients with a tracheostomy (criterion 16) would be unable to use the inhalation system. Patients that are currently receiving prostacyclin therapy (criterion 17) should be excluded to avoid the possibility of receiving excess prostacyclin therapy. Patients with a language barrier may have difficulty with instructions on how to use the inhalation device and with completing the follow up phone call. For exclusion criterion 19: Some patients with altered mental status may not be alert enough to complete the breathing pattern maneuver.

Enrollment, Randomization, and Study Initiation Time Window:

All inclusion criteria must be present concurrently. Patients must be enrolled within 24 hours of all inclusion criteria being met and identified. Information for determining when these time window criteria were met must be clearly documented.

Screening:

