We will also obtain a 4ml K_3 EDTA blood sample just prior to the Dose 1 drug administration on Day 3 to assess our trough level and another 4ml K_3 EDTA blood sample on Day 3 at 15 min (\pm 5 min) after the Dose 1 drug administration to assess our peak level In total, for the whole study duration, the maximum amount of blood that could be collected for the purpose of this study and in addition to the usual routine of medical care of care blood drawn is about 3.5 tablespoons. Peak and trough levels can also be obtained +/- one day to accommodate potential weekend blood draws.

Treprostinil or Placebo Administration:

Subjects will be treated using the Tyvaso® TD-100 Inhalation System. Oxygen will be delivered by nasal cannula or high flow nasal oxygen delivery system. Patients will be managed by an Oxygen Titration Protocol (See Appendix 3). Ampules of either active drug or saline (placebo) will be stored in blinded foil packs prepared and dispensed from Investigational Drug Services. Each will be labeled with a specific identifier that correlates with the randomization scheme. Once randomization occurs, the study coordinator will obtain the appropriate foil pack from IDS. The respiratory therapist will load the ampule into the TD-100 system. Remaining ampules will be stored in the foil pack to protect from light. The respiratory therapist will oversee the subject's administration of the drug, including the counting of the number of breaths taken. One ampule of drug will deliver 24 hours of medication or placebo. Ampules will be replaced every 24-hour period. On Study Day 00, during the Dose Escalation Phase, a blood pressure will be checked prior to Dose 1 and within 30 minutes after; prior to Dose 3 and within 30 minutes after; prior to Dose 5 and within 30 minutes after, or after a different dose interval, if the study drug had to be maintained due to an adverse effect. Blood pressure measurements for Study Days 01 through 11 will be captured from the nursing flow-sheets. The coordinators should document the blood pressure that was recorded as close as possible prior to the Dose 1 time frame for each study day. Arterial blood gas, systemic BP measurements, and central venous O2 saturation (if a CVC is in place) will be checked according to the schedule below (Table 2). Biomarker levels will be checked on Day 0, 3 and 7 as per Table 2.

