Cough or pharyngitis may occur with the administration of inhaled treprostinil. It is usually mild. The investigator may choose to utilize conservative measures such as topical throat lozenges/spray or non-narcotic based antitussive medications to improve compliance with drug administration.

All enrolled patients will receive standard medical care for their acute presenting illness regardless of randomization group, including but not limited to: antibiotics, IV fluids, supplemental oxygen, and any other needed diagnostic testing or imaging.

*Premature Withdrawal from Treatment:

The following adverse effects should prompt cessation of study drug:

- 1. A drop in oxygen saturation by >/= 10 percentage points, to an absolute value of < 90%, within 15 minutes of drug administration, regardless of apparent relationship to coughing.
- 2. Severe, intractable cough resulting in worsening hypoxemia and prolonged increase in O₂ requirement (Defined as an increase of more than 2LPM O₂ that closely correlates temporarily with the cough.)
- 3. Systemic hypotension requiring increase in vasopressor dose or initiation of vasopressors due solely to the administration of study drug (i.e. not due to underlying illness such as septic shock, as determined per the discretion of the investigator) despite titrating down to previously tolerated level.
- 4. Intubation and mechanical ventilator support
- 5. Need for Bi-level Positive Airway Pressure (BiPAP) or Continuous Positive Airway Pressure (CPAP) via face mask for worsening hypoxemia.

These patients will be followed out to study completion as defined by death, 28 days from randomization, or hospital discharge whichever comes first. Discharged subjects will receive a 28 day post randomization phone assessment of disease outcomes and adverse events.

Completion of Study Drug Administration:

Patients will be considered to have completed the study drug administration portion of the study and the study drug will be stopped when one of the following conditions is met, whichever comes first:

- 1. Up to 12 days after randomization (maximum treatment period)
- 2. Discharge from study hospital. Subjects will receive a 28 day post randomization phone assessment of disease outcomes and adverse events.

3. Death

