The optimal duration of treprostinil therapy for prevention of ARDS is not known. Since this is a prevention trial, a short time course of administration with rapid up titration and subsequent down titration of dose was chosen. Every 6 months or after 15 patients have completed the trial (whichever occurs first), an assessment of adverse events will be conducted by the DSMB, and recommendations for dose adjustments can be made.

Primary Endpoint

1) Change in PaO₂/FiO₂ ratio from day 0 to 2, 7

Secondary Endpoints

- 2) 28-day ventilator-free days
- 3) Need for Bi-level Positive Airway Pressure (BiPAP) or Continuous Positive Airway Pressure (CPAP) via face mask for worsening hypoxemia or High flow nasal cannula with a liter flow greater than 50LPM
- 4) Intubation and mechanical ventilation
- 5) Change in SpO₂/FiO₂ from Day 0 to Day 12 and on Day 28 if still hospitalized
- 6) Change in systemic biomarker concentrations from Day 0 to Day 7. Blood samples will also be banked for future analyses.
- 7) Change in SCVO₂ from Day 0 to 3 (if central venous catheter in place)
- 8) Change in CVP from Day 0 to 3 (if central venous catheter in place)
- 9) Change in MAP and Systolic blood pressure from cuff and/or arterial line (if placed) from Day 0 to 7
- 10) Pk studies/Plasma levels of treprostinil
- 11) 28-day mortality
- 12) Hospital mortality

Table 1: Schedule of Endpoint Assessments (See Appendix 2 for complete schedule)

	Day 0	Day 1	Day 2	Day 3	Day 4	Day 5	Day 6	Day 7
Biomarkers	Χ			х				х
PaO ₂ /FiO ₂	X (spot ABG)		X (spot ABG)					X (spot ABG)
SpO ₂ /FiO ₂	X	х	х	X	х	х	х	X to day 12and Day 28 if still hospitalized
SCVO ₂ (if CVC)	X	Х	х	х		Х		х

Version: 02-09-2018

RA/CVP (if	Х	х	х	х				
CVC)								
MAP (cuff)	Х	х	Х	х	Χ	х	х	х
MAP (a-line if	Х	Х	Χ	х				
placed)								
Syst. BP	Х	X	Χ	х	Χ	х	х	х
(cuff)								
Syst. BP (a-	Х	x	х	х				
line if placed)								

Data Collection

Background Assessments

- 1) Demographic and Admission Data
- 2) Pertinent Medical History and Physical Examination
- 3) Height; gender, measured body weight (MBW); calculated predicted body weight (PBW).
- 4) Type of Admission
 - a. Medical
 - b. Surgical scheduled
 - c. Surgical unscheduled
 - d. Trauma
- 5) Acute or Chronic renal failure and use of dialysis
- 6) Alcohol use
- 7) Survey of smoking history including:
- 8) Ever smoker (> 100 cigarettes in lifetime)?
- 9) If yes, current smoker?
- 10) Estimate of pack years (# packs per day) x (# years smoked)

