The following parameters will be measured and recorded using values closest in time to Dose 1 study drug administration on days 0-11 (depending on the specific variable), or until stopping of study drug, whichever comes first. All vascular pressures will be zero-referenced to the mid-axillary line with the patient supine.

- 1) Fluid intake and output (Twenty-four hour net fluid balance)
- 2) Vital signs: Heart rate, systolic and diastolic blood pressure, body temperature, CVP
- 3) Modified Brussels Score data days 0-14:
 - a) Vasopressor use (Y/N), worst systolic BP, creatinine, bilirubin, and platelet count for the day.
- 4) Presence of myopathy
- 5) Frontal Chest Radiograph Lung Injury Score (Days 0, 3, 7 and 28)
- 6) Concomitant medications, including nebulized and inhaled medications.
- 7) Blood banked for future analyses
- 8) Biomarker samples. Plasma obtained from two, 6 ml EDTA anti-coagulated blood samples will be divided immediately after centrifugation into 12 equal 1 ml aliquots in specified tubes and frozen at –80°C. Samples will be temporarily stored in the Pulmonary Division Lab space freezers in Burnett Womack Building or in the Emergency Room freezer. Specimens will be stored in the Koury Oral Health Sciences Building. Reference biomarker list above (Days 0, 3, and 7).

Statistical Considerations/Data Analysis:

Safety

Safety will be assessed via percentage of patients and number of events recorded for the following outcomes:

- Adverse events, serious adverse events, unanticipated problems, study discontinuation overall and due to adverse event, and deaths.
- Cases of dose intolerance, including cases of worsening oxygenation, intractable cough, and systemic hypotension following dosing
- Cases of intubation or noninvasive ventilation for worsening hypoxemia

Percentages of all outcomes above will be provided to the DSMB for regular unblinded review of safety, to be assessed every 6 months or after 15 participants have completed the 28 day trial or been discharged from the hospital (whichever occurs first).

Efficacy

Version: 02-09-2018

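### The Reference Measurements heading, read literally, ends Day 3 and Day 7 biomarker sampling when study drug stops, which conflicts with the unconditional biomarker schedule and with follow-up after withdrawal

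*Combined protocol and SAP*

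**What the plan says.** **The stop clause.** In the protocol, Reference Measurements, the opening sentence says that the listed parameters are recorded at the value nearest Dose 1 on days 0 to 11, depending on the variable, "or until stopping of study drug, whichever comes first". Item 8 of the list is the biomarker samples: "Reference biomarker list above (Days 0, 3, and 7".

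**Two items in the same list that run past the last drug day (Day 11).** "Modified Brussels Score data days 0-14" and "Frontal Chest Radiograph Lung Injury Score (Days 0, 3, 7 and 28".

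**The schedule without a condition.** Treprostinil or Placebo Administration: "Biomarker levels will be checked on Day 0, 3 and 7 as per Table 2". Table 1 and the biomarker row of Appendix 2 mark the same three days, also without an on-drug condition.

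**What stops study drug.** Premature Withdrawal from Treatment lists "Intubation and mechanical ventilator support", BiPAP or CPAP for worsening hypoxemia, post-dose desaturation, intractable cough with hypoxemia, and drug-related hypotension. Rationale for Exclusions agrees on ventilation: "Randomized patients are withdrawn from treatment if they require positive pressure ventilation". The text after the dosing schedule also lets the taper begin before Day 8 in patients who saturate adequately on room air, and ends drug on the day of discharge home.

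**Follow-up and endpoint.** Withdrawn patients are followed to death, Day 28 or discharge; blood sampling is not mentioned. The secondary endpoint is "Change in systemic biomarker concentrations from Day 0 to Day 7", which serves objective 4. The Efficacy section compares change from baseline by arm, overall and by whether lung injury had resolved by Day 28. It gives no rule for missing biomarker samples; the repeated-measures model is named only for PaO2/FiO2.

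**The concern.** Two instructions cover the same blood draw. One ends with study drug and the other does not. A coordinator with a patient intubated on Day 2 can defend either action from the text.

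The choice matters because the reasons for stopping drug are not neutral. Intubation and BiPAP or CPAP mark worsening disease, which these biomarkers are meant to reflect. Cough, desaturation and hypotension may be effects of the drug. Treatment could change the frequency of either kind of event. If the clause is applied, the patients with a Day 7 value are a group selected after randomization, and the comparison of arms is no longer protected by it. The planned stratum of patients whose lung injury had not resolved by Day 28 would plausibly lose most.

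**Working it through.** **1. Does the clause reach the biomarkers?**

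- Item 8 sits under it, and Days 3 and 7 fall inside days 0 to 11.
- The Brussels score (to Day 14) and the chest film (Day 28) cannot be governed by it, because their own days run past Day 11. So the clause does not bind every item. Biomarkers have no such later day to exempt them.
- The other places give days only. None says whether sampling continues off drug.
- In Appendix 2 the mark that ties rows to the Reference Measurements header stands on vital signs and not on biomarkers, so the table does not settle the question.
- The PaO2/FiO2 row in Appendix 2 carries a still-in-hospital condition. The biomarker row has no equivalent.

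The texts conflict and no sentence resolves them.

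**2. Which samples would go under the literal reading?**

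| Drug stops | Day 3 | Day 7 |
|---|---|---|
| Before Day 3 | lost | lost |
| Between Day 3 and Day 7 | kept | lost |
| After Day 7 | kept | kept |

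**3. Precision.** The plan gives no figure for biomarkers. Its only figure for 30 patients is for oxygenation: 80% power for the lower limit of an 80% interval to exceed 0 at an effect of 0.833 SD. It reproduces. With 20 and 10 patients the noncentrality is 0.833 / √(1/20 + 1/10) = 2.15, the t cut-off is 1.31 on 28 df, and the power is 0.80. Borrowing that effect size for a biomarker, as an illustration only, with equal loss in both arms:

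| Loss per arm | Active / control left | Power |
|---|---|---|
| 10% | 18 / 9 | 0.77 |
| 30% | 14 / 7 | 0.68 |
| 50% | 10 / 5 | 0.58 |

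**4. Bias.** The documents give neither stopping rates nor a correlation of severity with biomarker change, so both are assumed. Let severity be standard normal, its correlation with biomarker change be r = 0.3 to 0.6, and the treatment effect be zero. If a fraction f is lost at the severe end and g at the mild end, the mean of those left is shifted by

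r × [φ(z_g) − φ(z_(1−f))] / (1 − f − g), in SD units, with the first term 0 when g = 0.

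*Severe end only (g = 0).*
- f = 0.10: −0.1755 / 0.9 = −0.195
- f = 0.20: −0.2800 / 0.8 = −0.350
- f = 0.30: −0.3477 / 0.7 = −0.497

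With equal loss, each arm shifts by r × 0.350 to r × 0.497, that is 0.11 to 0.30 SD over the range of r, and the between-arm difference is 0. With 10% lost on active and 30% on control, the false difference is r × (−0.195 + 0.497) = r × 0.302 = 0.09 to 0.18 SD. Swapping the arms reverses the sign.

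A second model, with stopping logistic in the biomarker at log odds 1.0 to 1.5 per SD, gives 0.16 to 0.21 SD for the same 10% against 30%. For 25% on active and 10% on control it gives 0.12 to 0.16 SD the other way.

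*Both ends.*
- 30% lost at each end in both arms: the shift is 0 in each arm.
- 30% lost at the mild end in both arms, with 10% and 30% at the severe end: r × (0.3477 − 0.1755) / 0.6 = r × 0.287 = 0.09 to 0.17 SD.
- The higher-loss arm loses 30% at each end and the other 10% at each end: both shifts are 0 and nothing remains.
- One arm loses 10% severe and 30% mild, the other 30% severe and 10% mild: the shifts add, r × (0.287 + 0.287) = 0.17 to 0.34 SD.

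The sign and size of the net bias therefore turn on quantities that the plan does not give.

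**5. Scale.** With 18 active and 7 control patients left (10% and 30% lost), the standard error of a difference is √(1/18 + 1/7) = 0.45 SD. The 0.09 to 0.18 SD bias is less than half of that.

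**The case against.** The strongest reply is that this is a wording conflict and not an established loss of data. The same list contains items that outlast study drug, so item-specific days override the heading for at least two of them, and biomarkers also carry item-specific days. Three other places schedule Days 0, 3 and 7 plainly. The endpoint is exploratory, in a 30-patient feasibility trial, and any bias is small beside its standard error.

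Much of this stands. It cannot be said that the samples will be lost, only that the text permits it. The size is modest and rests on assumed rates.

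A reader might go further and infer that the biomarker comparison would keep only the milder cases. The documents do not support that. Drug also ends early in patients who recover or go home, some stopping events are intolerance and not severity, and a patient who fails between Day 3 and Day 7 keeps the Day 3 value. A reader might also extend the point to PaO2/FiO2 and SpO2/FiO2, but neither is in the Reference Measurements list.

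What does not stand is that the conflict resolves itself. The two items that escape the clause do so because their days lie beyond dosing; Days 3 and 7 do not. No text says that sampling continues off drug.

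**Conclusion.** The protocol contradicts itself on whether Day 3 and Day 7 biomarker samples are drawn after study drug stops. If the heading is followed, missingness depends on clinical course and possibly on arm. With equal severe-end loss there is no between-arm bias. With an assumed 10% against 30% it is roughly 0.1 to 0.2 SD, in a direction that depends on which arm loses more and that is unknown once early recoveries are counted. These figures rest on assumed stopping rates and an assumed link between severity and biomarker change.

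The consequence is limited to an exploratory secondary endpoint. It is still worth correcting before enrollment continues, because the remedy is a matter of collection and no analysis can recover a sample that was not drawn.

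**What to change.** In Reference Measurements and in Appendix 2, exempt biomarker samples from the stop clause. State that Day 3 and Day 7 samples are drawn in every randomized patient still in hospital, whether on or off study drug, and that they are timed to the study day when there is no Dose 1 to anchor them. No treatment rule changes.

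Patients discharged before Day 7 will still have no Day 7 sample. The Efficacy section should therefore say how missing biomarker values are handled, and the report should give the number of samples obtained by arm and day, with the reason for each one missing.

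The cost is a sentence in two places and a few already-scheduled blood draws in patients who are off study drug.

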- 14) Imminent need for intubation or non-invasive ventilation (patients that are requiring non-invasive ventilation soley for Obstructive Sleep Apnea are not excluded) (A high flow nasal cannula flow rate greater than 50LPM will be considered as an imminent need for positive pressure as well.)
- 15) Patient has comfort care orders written or otherwise will not receive supplemental oxygen including High Flow Nasal Cannula Oxygen Patient is Do Not Resuscitate/Do Not Intubate
- 16) Patient has a tracheotomy
- 17) Patient is currently receiving prostacyclin therapy [Epoprostenol (Flolan or Veltri) Iloprost (Ventavis) Treprostinil (Orenitram, oral) (Remodulin, IV or SC)]
- 18) Patient has a language barrier
- 19) Patient is unable to complete the breathing maneuver

Rationale for Exclusions:

Patients less than 18 years old are excluded because of limited clinical trial data with treprostinil in subjects younger than 18 years. Criteria 4, 8, 9, 13, 14 exclude patients unlikely to survive to the primary study endpoint or whose underlying condition or ventilator management complicates

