Analysis of covariance (ANCOVA) will be used to compare trends for the primary outcome PaO₂/FiO₂ ratio between days 0 and 7 between intervention and control patients. PaO₂/FiO₂ ratio is measured at baseline (day 0), and days 2, 7,. The difference in treatment groups for change from baseline to day 7 and days 2 will be estimated using an ANCOVA adjusting for baseline value. 95% and 80% confidence intervals for the difference in least squares means will be calculated. Due to small sample sizes, substantial normality departures due to skewness will be assessed. As a supportive exploratory analysis, if a number of patients do not have a day 7 assessment, a mixed linear model for repeated measures (MMRM) of PaO₂/FiO₂ ratio at days 0, 2, and 7 will be explored. The focus of the analysis is to assess preliminary evidence of efficacy. Sample size permitting, trends will be evaluated separately in trauma and non-trauma patients.

The secondary efficacy outcome, 28 day ventilator free days, is defined as days alive and free of mechanical ventilation during the first 28 days after randomization. Patients who die will receive 0 ventilator free days. Patients who are discharged free of mechanical ventilation prior to day 28 will be assumed to remain free of mechanical ventilation unless they are readmitted. Ventilator free days is expected to be skewed. Comparisons between treatment groups will focus on 95% and 80% confidence intervals of the Hodges-Lehman estimator for location shift.

Time until mechanical ventilation and time until death will be described via Kaplan-Meier survival curves.

Remaining efficacy outcomes and biomarkers will be analyzed with similar methods. Categorical outcomes will be characterized by odds ratios and assessed with chi-squared tests or Fisher's exact tests. Biomarker values change from baseline will be assessed comparing treatment groups overall and stratified by whether the acute lung injury was resolved by day 28.

Sample size calculation

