APPENDIX 2:

Schedule of Events

Description of Event	Day	Day	Day	Day	Day	Day	Day	Day	Day	Day	Day	Day	Day	Day	Day	Day
Description of Event	0	1	2	3	4	5	6	7	8	9	10	11	12	13	14	28
Inclusion / Exclusion Review	х															
Informed Consent	х															
Screening QTc	х															
Randomization	х															
Physical Examination	х															
Background Assessments	х			and Adr alysis U				story, He	eight; Ge	nder, M	easured	Body W	eight (M	l IBW); Ty	pe of Ho	spital
Baseline Assessments**	availa	ble for t	his 24 ho	our perio	d, the va	alue clos	est to th	hour int e time of measur	f randon	nization	will be re	ecorded.	If no va	lues are	availabl	
** Scoring (APACHE II and LIPS Scores)	х															
** Vital Signs and PaO ₂ ,PCO ₂ , pH; SpO ₂	х															
Available Labs ** Serum AST, ALT	х															
Required: ABG; Albumin; Bilirubin; BUN; Creat; Glucose; HCT; HGB; K; Na; Plt; WBC	х															
** Vasopressor or Inotropes Use	х															
Reference Measurements++	on the	specifi	c variabl		til stoppi	ng of stu		orded us , whiche								
Fluid Intake / Output	х	Х	х	х	х	х	х	х	х	х	х	х				
++ Vital Signs	х	х	х	х	х	х	х	х	х	х	х	х				
Concomitant Medication Use	х	х	х	х	x	x	x	x	x	x	x	x				
(Including Nebulized and Inhaled Medications)	^	^	^	^	^	^	^	^	^	^	^	^				
Lung Injury Score (Chest x-ray)	х			х				х								Х
Modified Brussels Score	х	х	х	х	х	х	х	х	х	х	х	х	х	х	х	
Study Drug Administration	х	х	х	х	х	х	х	х	х	х	х	х				
Blood Pressure Assessments (On Study Day 00, blood pressure will be checked prior to Dose 1 and 30 minutes after; prior to Dose 3 and 30 minutes after; prior to Dose 5 and 30 minutes or after a different dose interval, if the study drug had to be maintained due to an adverse effect. Blood pressure measurements for Study Days 01 through 11 will be captured from the nursing flow-sheets.	х	x	х	х	x	x	x	х	х	x	x	x				
Peak / Trough Specimen Collection (Peak Specimen will be obtained 15min [+/-5min] after Dose 1 on Day 3) (Trough Specimen will be obtained just prior to Dose 2 on Day 3)				х												

Biomarkers Specimen Collection	x			х				х						
(** Baseline specimen collection is prior to study drug administration)	^			^				^						
PaO ₂ / FiO ₂ Ratio (If the subject is still hospitalized)	х		Х					х						
SpO ₂ / FiO ₂ Ratio	х	х	х	х	х	х	х	х	х	х	х	х		Х
SCVO ₂ (if central venous catheter is in place)	х	х	х	х		х		х						
CVP (if central venous catheter is in place)	Х	х	х	х										

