SBP / MAP (if arterial line is in place otherwise cuff)	Х	х	х	х	х	х	х	х						
Adverse Events Review	х	х	х	х	х	х	х	х	х	х	х	х		
Hospital Mortality														х
Phone Assessment of Disease Outcomes and Adverse Events														х
Day 28 Mortality														Х

Version: 02-09-2018

Appendix 3

Oxygen Titration Protocol

The goal of the Oxygen Titration Protocol is to maintain a resting oxygen saturation of 90-94%. Brief increases in the research subject's O₂ liter flow for ambulation and exertion can be allowed. However, before each study drug administration, the respiratory therapist should make sure that the research subject is on the lowest amount of oxygenation required to achieve an oxygen saturation of 90-94% before recording their baseline O₂ requirement. Reassessment of oxygen saturation before and after each level should occur. Research subjects will start with a conventional humidified nasal cannula. If oxygen titration is needed, we will titrate from their current nasal cannula flow rate in the following stepwise fashion: 4LPM / 5LPM /6LPM. If there is a need for oxygen titration above 6 LPM, we will utilize a High Flow Nasal Cannula with the flow rate of 20 to 50 LPM. We will titrate the High Flow Nasal Cannula FiO2 in the following stepwise fashion: 50%, 60%, 70%, 80%, 90%, and 100%. The required liter flow will be titrated per patient need/demand. If a patient requires more than 50LPM via HFNC, they will have met our classification of *requiring positive pressure threshold*. If clinically indicated, clinicians that are managing the care of these research subjects can initiate non-invasive ventilation or proceed to intubate prior to a patient reaching 100% O₂ or 50LPM flow rate, per our stepwise fashion.

FiO₂ Conversion Table

FIU ₂ Con	version rable
Conventional Humidified Nasal Cannula Flow Rate	FiO ₂
1 LPM	24%
2 LPM	28%
3 LPM	32%
4 LPM	36%
5 LPM	40%
6 LPM	44%
High Flow Nasal Cannula Flow Rate	FiO ₂
20 LPM to 50LPM	50%
20 LPM to 50LPM	60%
20 LPM to 50LPM	70%
20 LPM to 50LPM	80%
20 LPM to 50LPM	90%
20 LPM to 50LPM	100%
	1

Version: 02-09-2018

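### The primary PaO2/FiO2 analysis has no rule for Day 2 and Day 7 values in patients who have progressed to BiPAP, CPAP or intubation

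*Combined protocol and SAP*

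**What the plan says.** In the combined protocol and SAP, under Statistical Considerations/Data Analysis, Efficacy, the P/F "ratio is measured at baseline (day 0), and days 2, 7", and the difference between arms "for change from baseline to day 7 and days 2 will be estimated using an ANCOVA adjusting for baseline value". The only provision for incomplete data is supportive and exploratory: "if a number of patients do not have a day 7 assessment, a mixed linear model for repeated measures (MMRM") is to be explored.

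Four other places bear on which values reach that analysis.

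- **Exclusion criterion 14** removes patients with "Imminent need for intubation or non-invasive ventilation (patients that are requiring non-invasive ventilation soley for Obstructive Sleep Apnea are not excluded"). Apart from that exception, baseline is off positive pressure.
- **Premature Withdrawal from Treatment** stops study drug for "Intubation and mechanical ventilator support", and for BiPAP or CPAP needed because hypoxemia worsens. It then says: "These patients will be followed out to study completion as defined by death, 28 days from randomization, or hospital discharge whichever comes first".
- **Appendix 2** schedules P/F on Days 0, 2 and 7 with one condition: "If the subject is still hospitalized".
- **Appendix 3** gives a saturation target of 90-94% and an FiO2 table. Both cover conventional cannula and high-flow cannula up to 50 LPM. For patients who need more than 50 LPM, "they will have met our classification of" needing positive pressure.

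A competing rule appears under Reference Measurements and again in Appendix 2: those measurements end when study drug ends. P/F is not in the Reference Measurements list.

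**The concern.** A gas drawn on a mask or ventilator is not like-for-like with a baseline gas drawn on cannula. The patient is off study drug, airway pressure can change PaO2 at a given FiO2, and FiO2 comes from the device and not from the Appendix 3 table. The plan itself treats these events as bad outcomes: they are secondary endpoints and safety outcomes.

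Unequal progression is also what the trial hopes to see. Its second hypothesis predicts a benefit on starting and duration of mechanical ventilation. If the arms differ in progression, the P/F comparison mixes the drug's effect on oxygenation with the effect of support, or else loses the failed patients altogether. With about 10 placebo patients, a single value carries real weight.

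**Working it through.** **1. The plan's own figures.** Inputs from Sample size calculation: changes of 15 and 10 (difference 5), SD 6, allocation 2:1, power 0.80, two-sided 0.05.

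- Control n = 1.5 × [6 × (1.960 + 0.842) / 5]² = 16.95, so 17 control and 34 active, as stated.
- At 20:10, SE = 6 × √(1/20 + 1/10) = 2.32. The probability that the lower 80% limit exceeds 0 is Φ(5/2.32 − 1.282) = 0.81, against the stated 80%.

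These figures are not in dispute. They are the yardstick.

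**2. Two readings of the silence.**

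| Reading | Basis | Progressed patient's P/F |
|---|---|---|
| A | Follow-up continues after withdrawal; the P/F row asks only that the patient be in hospital | Enters the ANCOVA as measured |
| B | Reference measurements end when study drug stops | Missing because the patient failed |

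A is likelier, because P/F has its own condition and is not in the Reference Measurements list. No sentence excludes B.

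**3. Leverage of one patient under A.** Let G be the amount by which a progressed patient's recorded change departs from the mean of the rest of the arm. The documents give no value, so ±20 to ±50 mmHg is assumed. Baseline adjustment is ignored for simplicity.

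Shift in (active − placebo) = G × (k_active/20 − k_placebo/10)

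| Progressed | G = +20 | G = +50 | G = −50 |
|---|---|---|---|
| 1 placebo, 0 active | −2 | −5 | +5 |
| 1 active, 0 placebo | +1 | +2.5 | −2.5 |
| 2 active, 0 placebo | +2 | +5 | −5 |
| 2 active, 1 placebo | 0 | 0 | 0 |

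**4. Precision.** Take arm variance as 36 + G²p(1 − p). With equal rates (2/20 and 1/10) there is no shift, but variance per patient is 72 at G = 20 and 261 at G = 50. The SEs are √(72/20 + 72/10) = 3.29 and √(261/20 + 261/10) = 6.26. At a true difference of 5, the probability of a lower 80% limit above 0 falls from 0.81 to 0.60 and 0.32. With no true effect and two progressed on active only, the nominal 0.10 becomes 0.30 at G = +20 and 0.48 at G = +50.

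**5. The sign.** Assume a baseline PaO2 of 65 at 4 LPM (table FiO2 0.36): 65/0.36 = 180.6.

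| On support (assumed) | P/F | Change |
|---|---|---|
| PaO2 85, FiO2 0.40 | 212.5 | +31.9 |
| PaO2 65, FiO2 0.50 | 130.0 | −50.6 |
| PaO2 70, FiO2 0.60 | 116.7 | −63.9 |

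To exceed baseline, PaO2 must pass 180.6 × 0.40 = 72.2, 180.6 × 0.50 = 90.3 or 180.6 × 0.60 = 108.3. Against the planned control change of 10, these examples give G of +21.9, −60.6 and −73.9, so ±50 is not a bound.

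**6. Under B.** If the progressed patient would have recorded a change 20 to 50 below the rest, leaving out one of 10 placebo patients raises that arm's mean by 20/10 to 50/10, or 2 to 5 mmHg. The MMRM would use an earlier value where there is one, but it assumes that the observed data explain the missingness.

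**The case against.** The strongest reply has three parts.

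**The treatment of these values is inferred.** A reader might infer that the plan analyses post-progression values as measured, so that failures count as oxygenation gains. The documents do not support that. They are silent, reading B remains open, and the ratio on support can fall as well as rise. Appendix 3 leads from 6 LPM (0.44) to high-flow oxygen at 0.50 or more before the positive-pressure threshold, although clinicians may escalate sooner. At such settings a loss is quite possible. This part stands in full.

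**Using values regardless of drug discontinuation is legitimate.** It is a treatment-policy choice, and on that view part of what looks like distortion is the answer to a different question. This stands too, but the plan does not say that it has made this choice.

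**Failures are not hidden.** Need for BiPAP/CPAP or high flow above 50 LPM, intubation and ventilator-free days are secondary endpoints. Intubation and non-invasive ventilation are safety outcomes, time to mechanical ventilation gets a Kaplan-Meier curve, and an intubation imbalance triggers DSMB review. This keeps the failures visible, but it does not correct the P/F estimate or its intervals. The trial's feasibility purpose lowers the stakes of the estimate without making it interpretable.

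**Conclusion.** The gap is real. The plan defines progression events that stop drug, keeps those patients in follow-up and schedules their P/F, and then gives no rule for the value. Under either reading the primary comparison can be distorted when progression differs between arms. Under reading A it also loses precision when progression does not differ.

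On an assumed departure of 20 to 50 mmHg per progressed patient, one placebo patient moves the difference by 2 to 5 mmHg and one active patient by 1 to 2.5, against a planned 5. These figures show leverage. How much of it is bias depends on the estimand, which is not stated.

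A reader might go on to infer a bias against the drug of a definite size. That would need progression rates by arm and an effect of support on the ratio. The documents give neither, so neither size nor direction can be fixed.

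**What to change.** 1. Reconcile Premature Withdrawal, Reference Measurements, Efficacy and Appendix 2 so that P/F is collected at Day 2 and Day 7 in every patient still in hospital, whether or not study drug has stopped. State the estimand that the ANCOVA addresses.
2. Record the support mode and the source of FiO2 with each P/F gas, including mask use for sleep apnoea, and tabulate both by arm. This is recording only and asks for no change in any patient's support.
3. Keep the mmHg ANCOVA with its 80% and 95% intervals, since the justification for 30 patients rests on it. Add to the Efficacy section a pre-specified rank ANCOVA on baseline for Day 2 and for Day 7. Deaths by that visit rank lowest. Next come patients who by then have met one of the plan's own progression events (intubation, BiPAP/CPAP for worsening hypoxemia, high flow above 50 LPM). All others rank by observed P/F.
4. Report the two side by side. Claim no oxygenation benefit from the ANCOVA alone if they disagree in direction.

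Patients discharged before a visit have no ratio and are not placed by this ranking. The plan should say how both analyses treat them.

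The cost is a small case report addition for support mode and FiO2 source, some wording and one more analysis, whose result is on ranks and not in mmHg.
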